5. STUDY DESIGN

This is a prospective non-randomised mechanistic study of 35 patients including a control group of 5 patients with SVT and 30 patients undergoing elective AF ablation.

The 30 patients undergoing AF ablation will include 10 who are undergoing elective AcQMap guided procedures in order to correlate non-contact propagation patterns with contact substrate mapping. These 10 patients will also undergo cardiac MRI before and after the ablation procedure.

The remaining 20 patients will also undergo electroanatomical voltage mapping using a contact force guided bipolar ablation catheter in order to compare the two methods/technologies. This is a non-blinded comparison study.

The 5 control patients will be undergoing elective catheter ablation procedures for left sided accessory pathways. Additional left atrial electroanatomical mapping will be performed to define normal electrophysiological properties for comparison.

Participants will be identified in clinic or after listing for the procedure. Screening and formal recruitment will then be undertaken, with the research study conducted during the ablation procedure. No follow up is required but participants undergoing AcQmap guided ablation and cardiac MRI will undergo a repeat cardiac MRI within 6 months following the procedure.

6. PARTICIPANT IDENTIFICATION

6.1. Study Participants

Patients with atrial fibrillation undergoing an elective catheter ablation procedure and 5 patients undergoing elective left sided catheter ablation involving a trans-septal puncture.

6.2. Inclusion Criteria

- Participant is willing and able to give informed consent for participation in the study.
- Male or Female, aged 18 years or above.
- Diagnosed with paroxysmal or persistent atrial fibrillation and planned for a catheter ablation procedure (AF ablation group only).

Date and version No: 9th March 2023, version 3.0

• Undergoing elective left sided catheter ablation procedure involving a trans-septal approach. (control group only)

• In the Investigator's opinion is able and willing to comply with all trial requirements.

6.3. Exclusion Criteria

- Previous cardiac surgery
- Medical history including any of: atrial fibrillation, atrial flutter, hypertension, diabetes mellitus, chronic obstructive pulmonary disease, significant mitral valve disease (stenosis or regurgitation), pulmonary hypertension, obstructive sleep apnoea, ischaemic heart disease, cerebrovascular disease, peripheral vascular disease, structural heart disease (excluding known accessory pathway), congenital cardiac anomaly (excluding accessory pathway), previous left atrial ablation (catheter or surgical), cardiac surgery (control group only)
- Contradictions to MR scanning (such as metallic or electronic objects implanted in your body or history of severe claustrophobia) (AcQMap guided ablation group)
- Significantly impaired renal function (eGFR<30ml/min)
- Female participant who is pregnant, lactating or planning pregnancy during the course of the trial.
- Any other significant disease or disorder which, in the opinion of the Investigator, may either put
 the participants at risk because of participation in the trial, or may influence the result of the
 trial, or the participant's ability to participate in the trial.
- Participants who have participated in another research trial involving an investigational medicinal product in the past 12 weeks. (Involvement in any other research trial is not a contraindication per se.)

7. STUDY PROCEDURES

7.1. Recruitment

Potential study participants will be identified by medical staff in the outpatient clinic at the time of listing for catheter ablation, or by review of patients electronically listed for this procedure. If patients are in the clinic and give consent then a member of the research team may approach them at this stage. Some members of the clinical team are also part of the research team and therefore if identified by medical staff through listing for the procedure, they will be approached by telephone. An information leaflet will then be provided by post or email if this has not been provided in clinic with contact details for the research team. If willing to participate then formal screening and recruitment will follow. For most, this will take place at the time of attendance for standard pre-procedure assessment appointments or when attending for the elective procedure. Participants undergoing elective AcQMap guided procedures and

requiring cardiac MRI, formal recruitment and consent will take place prior to the initial study MRI scan. Information must have been provided with sufficient time for the potential participant to fully consider involvement prior to formal recruitment and consent (generally expected to be at least 24 hours).

7.2. Screening and Eligibility Assessment

As there is no randomisation, there is no time limit between screening and formal recruitment. It is anticipated that these will occur at the same visit to coincide with standard clinical care and avoid an extra patient journey. Screening procedures include a review of medical history and demographics and recording of height and weight.

7.3. Informed Consent

The participant must personally sign and date the latest approved version of the Informed Consent form before any trial specific procedures are performed. It is anticipated that this is done at the initial visit, which will serve as both the screening and baseline study visit.

Written and verbal versions of the Participant Information and Informed Consent will be presented to the participants detailing no less than: the exact nature of the trial; what it will involve for the participant; the implications and constraints of the protocol; the known side effects and any risks involved in taking part. It will be clearly stated that the participant is free to withdraw from the trial at any time for any reason without prejudice to future care, without affecting their legal rights and with no obligation to give the reason for withdrawal.

The participant will be allowed as much time as wished to consider the information, and the opportunity to question the Investigator, their GP or other independent parties to decide whether they will participate in the trial. Written Informed Consent will then be obtained by means of participant dated signature and dated signature of the person who presented and obtained the Informed Consent. The person who obtained the consent must be suitably qualified and experienced, and have been authorised to do so by the Chief/Principal Investigator. A copy of the signed Informed Consent will be given to the participant and a copy placed in the medical records. The original signed form will be retained at the trial site.

7.4. Baseline Assessments

Baseline assessments include medical history; current medications and any recently stopped medications (with particular reference to anti-arrhythmic drugs and anticoagulants), smoking history, alcohol use, and illicit drugs use. Measurements taken should include height, weight and body mass index.

Data collected from imaging performed as part of standard clinical care should include left ventricular ejection fraction, diastolic function (including average E/E'), significant valvular disease (defined as at least moderate stenosis or regurgitation), left atrial diameter, left atrial volume (including indexed for body surface area), and presence of significant coronary disease at angiography (invasive or CT)(if performed).

Laboratory test results recorded should include haemoglobin, urea, creatinine, and creatinine clearance (estimated by Cockroft and Gault formula).

A 12 lead ECG should be performed.

7.5. Pre-procedure cardiac MRI

Those participants who are undergoing elective AcQMap guided ablation will undergo a cardiac MRI (3 Tesla) within the 6 weeks prior to the catheter ablation procedure.

Patients will complete an MRI safety questionnaire (5 min) prior to the scan. An intravenous cannula will be inserted. Cardiac MRI will evaluate cardiac structure and function, with particular focus on the left atrium. For late gadolinium enhancement imaging, the total dose of gadolinium-based contrast will not exceed 0.2mmol/kg.

The total duration of the MR protocol will be ~60 min, considering ~50 min of scanning time, plus ~10 min for pre-/post-scan preparation.

7.6. Study visit (control group)

As part of standard care, a 12 lead ECG will be performed for all patients following arrival on the day of their procedure.

Venous access, placement of electrophysiology catheters, and completion of diagnostic electrophysiology study will be undertaken in line with standard clinical care. Trans-septal puncture for left atrial access will be undertaken and anticoagulation will be administered in line with standard protocols. Prior to any ablation, left atrial electroanatomical voltage mapping (EAVM) using the Abbott Advisor HD Grid (SE) mapping catheter using the orthogonal wave setting (HD wave solution) will then be undertaken. This will be conducted during bipolar pacing from the mid point of the coronary sinus catheter at a cycle length of 800ms for 4 beats followed by a single extrastimulus with coupling interval of 300ms. Care must be taken to keep the catheter in each position to record all 5 cycles before moving to acquire new points aiming for a minimum of 300 points in total with full and equal covering of the atrial surface. Interpolation threshold should be set to 7mm with points filtered to within 5mm of the surface anatomy (interior and exterior projection). Initial map collection should be specified as a CFAE map set to collect points with the catheter stationary for 5 seconds.

Following completion of the EAVM, the procedure continues in line with standard clinical practice. If, for any reason the EAVM is not performed then the patient will be removed from the study. If mapping has commenced but is incomplete then the data will still be used.

7.7. Study visit (excluding control group)

As part of standard care, a 12 lead ECG will be performed for all patients following arrival on the day of their procedure. In line with standard practice in this institution all procedures will be undertaken under general anaesthesia.

Venous access, trans-septal puncture and placement of standard electrophysiology catheters will be undertaken as per standard clinical care. Anticoagulation will be administered following trans-septal puncture in line with standard protocols.

Please see appendix A for detailed study flow chart.

All patients

All study patients will undergo electroanatomical voltage mapping (EAVM) using the Abbott Advisor HD Grid (SE) mapping catheter using the orthogonal wave setting (HD wave solution) in the same manner as described above. If in AF at the start of the procedure direct current cardioversion (DCCV) will be used to restore sinus rhythm. This can be repeated at the discretion of the operator if initially unsuccessful (including internal cardioversion if necessary). If unsuccessful then the patient will no longer be included in the study and the procedure should continue according to standard clinical care.

Mapping will then be undertaken during bipolar pacing from the mid point of the coronary sinus catheter at a cycle length of 800ms for 4 beats followed by a single extrastimulus with coupling interval of 300ms (or the shortest captured cycle length if longer). Atrial geometry can be acquired concurrently. Care must be taken to keep the catheter in each position to record all 5 cycles before moving to acquire new points aiming for a minimum of 300 points in total with full and equal covering of the atrial surface. Interpolation threshold should be set to 7mm with points filtered to within 5mm of the surface anatomy (interior and exterior projection). Initial map collection should be specified as a CFAE map set to collect points with the catheter stationary for 5 seconds. Subsequent analyses offline will use the Precision turbomap feature to adjust the data displayed. Ablation and the rest of the procedure can then be performed according to standard clinical practice.

Post procedure care including subsequent discharge will continue in line with standard clinical practice.

Subgroup undergoing contact force guided mapping

20 patients undergoing AF ablation will have a further map completed using a contact force guided bipolar irrigated ablation catheter (Abbott Tacticath) during the same pacing protocol. For all voltage maps a minimum of 300 points should be obtained with full and equal covering of the atrial surface, interpolation should be set to 7mm, and set to only include points with contact force between 5 and 50grams.

Subgroup undergoing AcQMap guided mapping and ablation

10 patients with persistent AF who are undergoing AcQMap guided elective catheter ablation procedures will be included in this sub-study. All patients will undergo the same main study mapping procedure outlined above. In addition, AcQMap recordings will also be obtained. Recordings will be made during pacing with the same main study protocol and two 30 second recordings will be undertaken during AF. HD grid contact recordings will then also be obtained in regions of prominent rotational and irregular conduction identified by AcQMap and ablation performed at the operator's discretion.

For patients presenting in sinus rhythm or AF, all required mapping should be completed in the presenting rhythm followed by either AF induction (using incremental burst atrial pacing) or DCCV respectively before completion of mapping procedures. Ablation in line with standard clinical care will be undertaken following completion of all mapping procedures.

For an outline of study procedures versus standard care and estimated time requirements, please see appendix B.

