The HD grid catheter is still a traditional "point by point" mapping system whereby small areas of the atrium are examined in sequence. Non-contact dipole density mapping facilitated by the AcQMap system from Acutus Medical allows real-time visualisation of whole chamber activation during AF and reveals complex propagation patterns. These patterns are highly variable between patients and their detailed analysis may identify important patterns related to the underlying electrophysiological substrate that may further our understanding of AF mechanisms and help guide effective ablation strategies.

This study therefore aims to conduct detailed EAVM using the Abbott HD grid catheter in 5 control patients undergoing ablation of left sided accessory pathways who are thought to have normal atria in order to define normal voltage amplitude and the response to changing activation rate. Detailed EAVM will then be performed in patients undergoing catheter ablation for AF in order to evaluate atrial properties at both long and short pacing cycle lengths. In 2 separate subgroups, the orthogonal HD grid mapping will be compared to either AcQMap propagation patterns or to a conventional bipolar ablation catheter with contact force. It is hypothesised that regions of intermediate voltage will demonstrate exaggerated slowing in conduction velocity and broadening of electrograms with shortening cycle length compared to regions of preserved amplitude, which will correlate with regions of slow and irregular propagation patterns during atrial fibrillation and late gadolinium enhancement on cardiac MRI. Furthermore, EAVM using the HD grid catheter will reveal higher mean electrogram amplitude compared to bipolar mapping with a lower surface area identified as low voltage (<0.5mV). The improved mapping resolution provided by the HD wave solution and HD grid catheter alongside use of varying activation times will facilitate greater understanding of the variable and patient specific AF substrate involved in AF maintenance. It is anticipated that combining this with non-invasive assessment of fibrosis distribution through cardiac MRI and AF propagation patterns visualised by panoramic mapping will provide pilot data with the potential to identify sub-groups of AF phenotypes. This data can then be applied to larger multi-centre studies of substrate mapping to better characterise the arrhythmic substrate and develop patient specific ablation strategies.

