9. STATISTICS AND ANALYSIS

9.1. Description of Statistical Methods

This is a mechanistic study exploring a change in electrogram morphology. This will be expressed as a proportion of signals recorded within each amplitude bracket. Statistical comparisons using the chi-square tests of 2 proportions will be made to look for significant differences at long and short cycle length.

In the sub-study comparing voltage mapping methods, simple statistical analysis will be used to compare voltage amplitudes obtained by each method in sinus rhythm and in AF. Means will be compared using independent sample t-test.

Retrospective analyses may be conducted to explore trends in electrophysiological mechanisms identified and their relation to demographic, anatomical, or clinical features recorded and in line with secondary outcome measures.

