16. APPENDIX A: PARTICIPANT GROUP ALLOCATION AND STUDY FLOW CHART

17. APPENDIX B: Table distinguishing routine and study procedures and estimated additional time requirements

Standard care			Research procedure				
All elective AF ablation patients	AcQMap guided AF ablation patients	Left sided accessory pathway ablation	5 control patients	30 AF patients	Contact-force mapping subgroup	AcQMap guided subgroup	
Venous access and insertion of electrophysiolo gical catheters and trans- septal puncture	Additional venous access and insertion of AcQMap catheter	Venous access and insertion of electrophysiol ogical catheters	Specified left atrial 3- dimensional mapping using HD grid and specified study protocol (Additional time estimate = 20 minutes)	Specified pacing map during initial left atrial 3-dimensional mapping and geometry acquisition using HD grid (Additional time estimate = 10 mins)	Additional ablation catheter map during pacing (Additional time estimate = 15 minutes)	AcQMap recording during pacing (Additional time estimate = 5 minutes)	
Standard 3- dimensional left atrial geometry acquisition and contact mapping using a multipolar mapping catheter	AcQMap mapping of AF (left +/- right atrium	Trans-septal puncture				HD grid catheter evaluation of regions with specified activation patterns (Additional time estimate = 10 minutes)	
Direct current cardioversion (if clinically required)	Additional left +/- right atrial ablation	Diagnostic EP study				, and the second	
Left atrial ablation including pulmonary vein isolation		Accessory pathway mapping and ablation					
Total additional t	time estimates foi	each study	20 minutes	10 minutes	15 minutes	15 minutes	

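### In the 20-patient catheter comparison the HD grid map appears always to come first, so any voltage change between the two maps is counted as a catheter difference

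*Combined protocol and SAP*

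**What the plan says.** All AF patients have the HD grid voltage map. Section 7.7 adds for those not in sinus rhythm: "If in AF at the start of the procedure direct current cardioversion (DCCV) will be used to restore sinus rhythm". In the subgroup, "20 patients undergoing AF ablation will have a further map completed using a contact force guided bipolar irrigated ablation catheter", and this is done "during the same pacing protocol".

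The Appendix B table of routine and study procedures describes the HD grid step for AF patients as "Specified pacing map during initial left atrial 3-dimensional mapping and geometry acquisition using HD grid". It describes the subgroup step as "Additional ablation catheter map during pacing", with an estimated 15 extra minutes.

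Section 3 states the hypothesis: "EAVM using the HD grid catheter will reveal higher mean electrogram amplitude compared to bipolar mapping". It also predicts a smaller low-voltage area.

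On analysis, section 9.1 says "Means will be compared using independent sample t-test". Section 9.3 adds the difference between each ablation-catheter point and its nearest HD grid point, averaged over the chamber and by segment. Neither section has a term for map order, period or time since cardioversion. Section 5 describes the study as non-randomised and the comparison as non-blinded, and no readable text balances the order of the two maps.

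**The concern.** Each of the 20 patients is mapped with both catheters in one session, so this is a two-period within-patient comparison. If every patient has the same order, the difference between catheters is also the difference between an earlier and a later map. Possible sources of change between maps include recovery after cardioversion, anaesthesia, fluid from the irrigated catheter, contact from the first catheter and shift of the map. These are suggestions; the documents do not discuss them.

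The direction matters because section 3 predicts one. A fall in recorded voltage between the maps would produce the predicted HD grid advantage; a rise would hide it. Only patients who arrive in AF are cardioverted just before the first map, so any change could also differ between patients.

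**Working it through.** **Is there a figure to reproduce?** No. Section 9.2 gives no effect size, SD or power for this comparison. The counts agree: 20 + 10 + 5 = 35.

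**Step 1: the order.** Section 7.7 has the HD grid map for all AF patients and then a *further* map in the subgroup. Appendix B (section 17) has HD grid during *initial* mapping and geometry acquisition, and the ablation-catheter map as *additional*. The schedule in section 18 lists mapping with both catheters in one row without a sequence. The natural reading is HD grid first throughout, but no sentence states it as a rule.

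**Step 2: what the comparison estimates.** Let c be the true HD-minus-ablation difference and π the change in recorded voltage from first to second map.

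- HD grid first: expected difference = c − π.
- Ablation catheter first: expected difference = c + π.
- Fixed order: only c − π is observed, so c and π cannot be separated. A paired test removes the patient effect but leaves π. A period term cannot be estimated.
- 10/10 order: the average of the two order-specific means is [(c − π) + (c + π)]/2 = c.

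**Step 3: size in mV.** Assumed, not in the documents: between-patient SD 0.5 mV, SD of the within-patient difference 0.3 mV, two-sided alpha 0.05. Simulated means of the estimate for n = 20:

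| True c (mV) | π (mV) | Fixed order | 10/10 with period term |
|---|---|---|---|
| 0 | −0.1 | 0.10 | 0.00 |
| 0 | −0.2 | 0.20 | 0.00 |
| 0.3 | −0.2 | 0.50 | 0.30 |
| 0.3 | +0.2 | 0.10 | 0.30 |

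**Step 4: illustrative false-positive rates.** Here c = 0, the patient is the unit, d is the absolute change in between-patient SDs and ρ is the within-patient correlation; both are assumed. For the paired test the non-centrality is d√20 / √(2(1 − ρ)). For example, d = 0.5 and ρ = 0.5 give 0.5 × 4.472 / 1 = 2.24, and rejection in 57%. The independent-test rates are simulated.

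| d | Paired, ρ 0.5 | Independent, ρ 0.5 | Paired, ρ 0.8 | Independent, ρ 0.8 |
|---|---|---|---|---|
| 0 | 5% | <1% | 5% | <1% |
| 0.1 | 7% | 1% | 10% | <1% |
| 0.2 | 14% | 3% | 27% | <1% |
| 0.3 | 25% | 8% | 52% | 2% |
| 0.5 | 57% | 29% | 92% | 22% |

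The plan names the independent test. It is conservative here because it ignores the pairing, but its estimate carries the same bias as the paired one. With a 10/10 order and a period term, rejection stays at about 5% at every change tried.

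**Step 5: price of the period term.** Degrees of freedom fall from 19 to 18, and the critical t rises from 2.09 to 2.10.

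**The case against.** The strongest reply has four parts.

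- **Order.** It is inferred. *Further* and *additional* could mean extra to routine care, and section 7.7 sends the reader to Appendix A for the detailed flow. This stands as a limit: if that chart alternates the order, the concern falls.
- **Drift.** None is shown. The two maps share a session, general anaesthesia and a pacing protocol, and the second takes about 15 minutes. This also stands: the change may be small. The plan, however, neither argues this nor provides for measuring it.
- **False positives.** A reader might infer that the comparison as planned has a badly inflated error rate. The documents do not support that. The large rates in Step 4 belong to a paired test that the plan does not name. The named test at patient level stays at about 8% or below for changes up to 0.3 SD. Treating 20 × 300 = 6,000 points per catheter as independent gives 78% for a change of only 0.05 point-SD, but that is mainly pseudoreplication, a separate defect.
- **Balance.** A reader might infer that alternating the order removes all bias. It removes an additive change only. Irrigation fluid comes from one catheter, contact effects may depend on which catheter went first, and a reversed order could change which catheter builds the geometry and so affect nearest-point matching.

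It is also fair that this is one secondary outcome in an exploratory study. The primary outcome uses the control group and is unaffected.

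**Conclusion.** The point holds as a bias in the estimate. On the natural reading of section 7.7 and Appendix B, catheter and map order are fully confounded in all 20 patients. The estimated HD grid advantage equals the true one minus any first-to-second change in voltage, and neither a paired nor an independent test can recover the catheter effect.

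This rests on the inferred order. The size and direction of any change are unknown; the mV figures and rejection rates are illustrations under assumed inputs. A reader might go further and infer that an observed HD grid advantage would be an artefact of time. The documents give no evidence for that; they show only that the two explanations could not be told apart. The remedy is a cheap improvement to the subgroup and leaves the rest of the study as it is.

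**What to change.** **Section 7.7.** State the sequence of the two maps and that both are completed before ablation. At present the sentence placing ablation after all mapping sits under the AcQMap subgroup, so it does not expressly cover these 20 patients. Where workflow allows, alternate or randomise which voltage map comes first (10 HD grid first, 10 ablation catheter first), keeping the geometry method the same in both orders.

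**Sections 9.1 and 9.3.** Analyse patient-level paired differences with a period term: the catheter effect is the average of the two order-specific mean differences. Report the result by whether the patient was cardioverted before mapping. Note that balance removes additive drift but not catheter-specific carry-over.

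**If the order must stay fixed, or for patients already mapped.** Record the time of each map and report a first-map (HD grid) versus second-map (ablation catheter) difference, saying that catheter and order cannot be separated.

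**Cost.** No extra patients, maps or staff. The mapping workflow changes in about 10 patients, possibly with an extra catheter exchange, because the HD grid map currently doubles as geometry acquisition. The analysis loses one degree of freedom.
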